**The primary aims:**

- 1) Evaluate the safety and acceptability of the R-VR
- 2) Evaluate the adherence to the R-VR
- 3) Evaluate the impact of using R-VR on anxiety and inattention levels
- 4) Compare the impact of two R-VR paradigms on anxiety and to correlate this impact with baseline self-efficacy

The major constructs that will be examined in this proposal are (1) Safety; (2) Anxiety; (3) Inattention; (4) Self-Efficacy. It is expected that this exploratory work will lay the foundation for future studies on anxiety and inattention interventions at work.

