### Study Design and Methods

**Design:** This is a single blinded randomized cross-over study. The participants will be randomly assigned the order of the paradigms viewed in the R-VR or as videos on the computer. The randomization will be through REDCap, as programmed by the study statisticians. The R-VR with the pre-programmed paradigms and corresponding non-VR videos will be labelled A through D. The coordinators will be informed via REDCap about which the experience to provide the participants for each of the study visits: A-D for Visits 1-4.

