## Visit Flow and Timeline

Visit Number	Day 0	Day 1		Day 4		Day 7		Day 10	
	V0 	V1a 	V1b	V2a	V2b	V3a	V3b	V4a	V4b
		Consent + 0 day to +7 days from	Immediately following VR/Video	Prior to VR/Video	Immediately following VR/Video	Prior to VR/Video	Immediately following VR/Video	Prior to VR/Video	Immediately following VR/Video
Informed Consent	X 								
Inclusion/Exclusion	X								
Demographics Form	X								
Medical History	X								
Adverse Events	X	X		X		X		X	
Concomitant Medications	X	X		X		X		X	
R-VR Intervention			X		X		X		X
Brief Resilience		X		X		X		X	
Evaluate Response to the VR experience (HUMAN)		X	X	X	X	X	X	X	X
Emotional distress		X	X	X	X	X	X	X	X
Cognitive Function		X	X	X	X	X	X	X	X
Self-efficacy		X		X		X		X	
Anxiety		X	X	X	X	X	X	X	X
Satisfaction Survey									X

Consent can be completed digitally in person or through remote consenting

Visit 0 and Visit 1 can occur on same day or on separate occasions at the participant's convenience.

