## Assessments

### Study Entry Screen/Safety:

- Demographics Form: This form will collect demographics (age, sex, education, marital status, job title), and other lifestyle history of the research participant.
- Medical History Form: This form will collect history of comorbid conditions such as head injury, seizures, major mental illness or anything that could interfere with the VR experience (e.g. eye sight). This information will be collected via self-report and health record abstraction.
- Adverse Events: Pre-post measures will be obtained for dizziness; stomach awareness; headaches; eyestrain and lightheadedness; nausea; seizures in individuals with photosensitivity; disorientation; temporary (short term) loss of spatial awareness.
- Concomitant Medications: Current medications (name, dosing, and indications) will be collected at every patient encounter.

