## **Video Experience Procedure**

Participants will be scheduled for a 30-min office visit. After a verbal description of the study process and completion of IRB consent form, participants will complete the demographic and other baseline questionnaires.

The coordinator will instruct the participant on certain procedures dependent on the study participant's randomization and visit:

**R-VR Experience:** Study participant will be asked to complete a set of questionnaires, following completion they will be seated in a swivel chair in the center of the research room, given basic instruction on the VR headgear [*Oculus Quest*], and then offered the opportunity to experience the intervention event. The approximately 10 minute VR event involves one of two scenes (randomly selected by REDCap): Scene 1 is designed for relaxation in nature with natural scenery such as trees, streams and deer, or Scene 2 designed to help the participant focus with natural scenery such as glowing embers and fireflies. After a VR experience, the headgear will be removed and the participants will be asked to complete a second round of questionnaires.

**Computer Video Experience:** Study participant will be asked to complete a set of questionnaires, following by being seated at a computer and asked to watch a video with one of two scenes: (Scene 1) natural scenery such as trees, streams and deer; (Scene 2) natural scenery such as glowing embers and fireflies. After this viewing they will be asked to complete a set of surveys.

All will be remunerated up to \$40 at the end of their study participation. This amount will be prorated based on the number of visits completed

This process will provide a within-participant control, allowing us to investigate whether the VR experience is safe and results in significantly more change than the Video experience.

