### Data Analysis

**Power Statement:** The sample size for this pilot investigation (N=24) was established after considering both the statistical implications and the amount of project effort and resources required to recruit and study this unique participant population.

**Data Analysis Plan:** Data related to participant recruitment will be summarized, including the frequency of calls and the reasons for failing screening criteria. In all cases, data will be summarized using mean  $\pm$  SD for continuous variables and frequency percentages for nominal variables. Details will be documented and summarized for any participants who experience adverse events or are unable to complete the 10-minute VR experience for any reason. The percentage of participants who undergo the initial VR experience (V2) but discontinue study participation without returning for the 2nd VR experience (V3) will be summarized and compared between scenes using Fisher's exact test. Anxiety, stress, cognition will be assessed immediately before/after and 24 hours following each VR experience. Within and between group comparisons will be performed using appropriate repeated measures analyses (e.g. paired t-test, repeated measures ANOVA) taking into account the two group repeated measures cross-over study design. In all cases, findings will be summarized using point estimates and corresponding 95% confidence intervals.

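### The adverse event summary does not separate VR from video or from pre-existing symptoms, and the schedule lacks the post-session collection that the assessments text promises

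*Combined protocol and SAP*

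**What the plan says.** The first primary aim is to "Evaluate the safety and acceptability of the R-VR". Video Experience Procedure explains how the design serves that aim: it gives a "within-participant control, allowing us to investigate whether the VR experience is safe". Study Design and Methods states that "The participants will be randomly assigned the order of the paradigms viewed in the R-VR or as videos on the computer", with REDCap issuing "A-D for Visits 1-4". Each person therefore has both VR scenes and both matching videos, and only the order varies.

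Three places deal with AEs:

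- **Assessments, Study Entry Screen/Safety:** "Adverse Events: Pre-post measures will be obtained for dizziness; stomach awareness; headaches; eyestrain and lightheadedness; nausea", followed by further symptoms.
- **Visit Flow and Timeline:** the row "Adverse Events X X X X X", with the five marks at V0, V1a, V2a, V3a and V4a. The last three columns are headed "Prior to VR/Video". The intervention itself is marked in the 'b' columns.
- **Data Analysis:** "Details will be documented and summarized for any participants who experience adverse events or are unable to complete the 10-minute VR experience". Nothing else in that section concerns AEs.

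**The concern.** The protocol relies on video to show whether VR is safe, but the AE analysis never mentions video. It identifies participants with events. It does not say which experience came before each event, or whether the symptom was already there. Headache, eyestrain, dizziness and nausea can be present before any session, so a count of affected participants mixes three sources: pre-existing symptoms, symptoms after video and symptoms after VR.

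The data collection is also unclear. A measure taken after the session at the same visit would give a direct change for each experience. The assessments text promises this, but the schedule does not provide for it.

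Aims, purpose, or objectives says the pilot will decide whether a larger study with longer daily VR is developed. A safety result that does not isolate VR is a weak basis for that decision.

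**Working it through.** The plan gives no AE rate, power or comparison, so there is no stated figure to reproduce. The check has two parts: a count from the schedule, and an illustration with assumed rates.

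**1. What the schedule covers**

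Inputs: 24 randomised participants (Participant Information), four sessions each (Study Design and Methods), AE marks from Visit Flow and Timeline.

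| AE mark | Position | Session it can follow |
|---|---|---|
| V0, V1a | before any exposure | none (baseline) |
| V2a | before session 2 | session 1 |
| V3a | before session 3 | session 2 |
| V4a | before session 4 | session 3 |
| none | after session 4 | session 4 has no later mark |

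- Sessions: 24 × 4 = 96, of which 24 × 2 = 48 are VR.
- Sessions followed by a scheduled AE mark: 24 × 3 = 72.
- Sessions with no later mark: 96 − 72 = 24, a quarter of the total. If order is balanced (an assumption, since the documents do not state it), half of these, 12, are VR. That is 12 of the 48 VR sessions.
- On the nominal Days 1, 4, 7 and 10, each mark that does follow a session comes 3 days later. None falls after a session at the same visit.

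**2. Schedule against assessments text**

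The schedule shows how a before-and-after instrument is marked: anxiety, emotional distress, cognitive function and the HUMAN form are ticked in both 'a' and 'b' columns. Resilience and self-efficacy are ticked in 'a' only. AEs follow the second pattern, although the assessments text describes the first. The two sections disagree.

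**3. What a per-participant count can distinguish**

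Let p be the event probability per session, assumed equal for VR and video and independent across sessions. The share of participants with any event over four sessions is 1 − (1 − p)^4. If instead all events come from VR, at probability v over two VR sessions, the share is 1 − (1 − v)^2. The two are equal when v = 1 − (1 − p)^2.

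| Same rate p in VR and video | VR-only rate v (video 0%) | Participants with any event, either case | Expected of 24 |
|---|---|---|---|
| 5% | 9.75% | 18.5% | 4.5 |
| 10% | 19.0% | 34.4% | 8.3 |
| 20% | 36.0% | 59.0% | 14.2 |

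For p = 10%: 1 − 0.9^4 = 1 − 0.6561 = 0.344; v = 1 − 0.9^2 = 0.19; 1 − 0.81^2 = 0.344. In each row, a trial with no VR effect and a trial in which VR causes every event give the same headline count. The rates are assumptions. The equality holds at any p under this model.

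**The case against.** A reader might infer that the trial cannot show what VR caused. The documents do not support that. REDCap issues the experience for every visit, so reports at V2a, V3a and V4a can be linked to the session before. If the promised before-and-after measures are taken, they give a change within each visit. Attribution is feasible; the plan does not specify it.

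A reader might also infer that events will be filed under the wrong experience, because a report at one visit concerns the session at the previous one. No section says AEs will be read by visit label, so a misfiling rate would describe an error that nobody has planned.

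Collecting AEs at V0 and V1a is sound. It is a baseline, and the only fault is that the analysis does not treat it as one. Because V0 and V1 may fall on the same day, these two marks should not be counted as reliably separate opportunities for an event.

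The analysis sentence can be read as saying only whose events will be described, and such descriptions could include timing and experience received. That is fair, and in a trial of 24 a careful listing might recover much of the information. But the sentence does not require it. The repeated-measures sentence does not fill the gap either: it follows a list of anxiety, stress and cognition, and AEs are not named. The same list mentions a 24-hour assessment, but not for AEs, and the schedule shows none.

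The AE marks match those for concomitant medications, which are collected at every encounter, so an 'a' mark might simply mean once per visit. That is possible, but once per visit is still not before and after.

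Failure to finish the VR experience can be read alone as a tolerability measure. Setting it beside video is a low-cost improvement, and its absence is not an error.

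Finally, this is a pilot. Even no events in 24 participants leaves an upper two-sided 95% limit of 1 − 0.025^(1/24) = 14.2%. The request is therefore for a clear descriptive table and not for power.

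**Conclusion.** The point holds as a gap in the analysis plan together with a conflict between two sections. As written, the AE summary does not separate VR from video or from symptoms present before exposure, although video is named as the control for safety, the first primary aim. The schedule leaves 24 of 96 sessions without a later AE mark. The 24 is a direct count. The figure of about 12 VR sessions rests on balanced order. The paired rates in the table are illustrations under assumed, independent probabilities and do not predict what this trial will see. The change should be made before the data are summarised, and the collection part before the visits take place.

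**What to change.** - **Reconcile Visit Flow and Timeline with Assessments:** mark the AE and symptom form at the existing 'b' assessments V1b to V4b, so that the last session is covered.
- **Baseline:** treat V0 and V1a reports as baseline. For the safety result, count a listed symptom when it is new or worse than the level before that session. Keep all reports, including baseline ones, in the listing.
- **Attribution:** record onset date and time. Link events found between visits to the last experience received before onset, using the REDCap sequence and not the visit number. This matters because Data Analysis ties the first and second VR experiences to V2 and V3, which does not fit a random order over four visits.
- **Data Analysis:** tabulate AEs and non-completion by experience received (VR scene 1, VR scene 2, video 1, video 2). For each participant, take the proportion of VR sessions with an event minus the proportion of video sessions with one, and report the mean with its 95% CI. The section already commits to estimates with 95% intervals. State the interval method in advance, since events may be few.

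Cost: a short form repeated at post-session assessments where participants already complete questionnaires, one or two extra fields for onset, and some rewording. No visits or participants are added and the sample size is unchanged. The downside is a small added burden and an 'unassigned' row for events with unclear onset.

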#### Acceptability and Adherence to Intervention:

- Acceptability will be measured through the patient satisfaction survey at the end of the study.
- Adherence to the R-VR will be assessed by collecting attendance for study visits 1-4.

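### The VR drop-out comparison ties the first and second VR sessions to V2 and V3, although session order is randomised over Visits 1-4

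*Combined protocol and SAP*

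**What the plan says.** The Data Analysis Plan defines the measure as follows: "The percentage of participants who undergo the initial VR experience (V2) but discontinue study participation without returning for the" second session, and continues "VR experience (V3) will be summarized and compared between scenes using" Fisher's exact test. The first VR session is thus placed at V2 and the second at V3 for everyone.

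Other sections describe a different layout:

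- Study Design and Methods, Design: "The participants will be randomly assigned the order of the paradigms viewed in the R-VR or as videos on the computer". It adds "The R-VR with the pre-programmed paradigms and corresponding non-VR videos will be labelled A through D", and coordinators learn from REDCap "which the experience to provide the participants for each of the study visits: A-D for Visits 1-4". That makes four conditions, one per visit.
- Visit Flow and Timeline: sessions fall on Days 1, 4, 7 and 10, and each of V1 to V4 has a column headed "Immediately following VR/Video". No visit is marked as VR only or video only.
- Video Experience Procedure: what happens at a visit depends on the participant's randomisation and on the visit.
- The primary aims include "Evaluate the adherence to the R-VR", and the adherence section states "Adherence to the R-VR will be assessed by collecting attendance for study visits 1-4".

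**The concern.** The words initial and second VR experience make sense under a randomised order, because each participant has a first and a second VR session. The visit labels do not: under a randomised order, those sessions fall at different visits for different people. The plan therefore contains two definitions that count different participants, and does not say which governs.

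If the labels govern, two kinds of leaver are always left out:

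- a participant whose first VR session is at V1 and who leaves before V2;
- a participant whose second VR session is due at V4 and who leaves after attending V3.

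If everyone at V2 is counted, the measure also takes in people who have already had both VR sessions or have had neither. Adherence is a primary aim, and this is the only attendance-based comparison that the analysis section names. Its definition should be settled before drop-outs are known.

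**Working it through.** The plan gives no figure to reproduce here. N=24 comes without a drop-out rate, alpha or power.

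**Inputs.** From the documents: 24 randomised; four conditions (two VR, two video); one condition per visit over V1-V4. Assumed: all 4! = 24 orders equally likely, with one participant in each; a constant probability d of leaving after each visit, with d from 2% to 20%. Write q = 1 - d.

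**Step 1: where the two VR sessions fall.** There are six possible pairs of visits, each arising in 4 of the 24 orders.

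| VR visits | Orders | Both labels right? |
|---|---|---|
| V1, V2 | 4 | no |
| V1, V3 | 4 | no |
| V1, V4 | 4 | no |
| V2, V3 | 4 | yes |
| V2, V4 | 4 | no |
| V3, V4 | 4 | no |

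The first VR session is at V1 in 12 orders, V2 in 8 and V3 in 4. Both labels are right in 4 of 24 (16.7%).

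**Step 2: true leavers.** A true leaver stops after visit k, with the first VR session at or before k and the second after k. Orders that qualify:

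- k = 1: 12 (first VR at V1);
- k = 2: 16 (V1-V3, V1-V4, V2-V3, V2-V4);
- k = 3: 12 (second VR at V4).

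Expected true leavers = d(12 + 16q + 12q²). The share leaving between V2 and V3 is 16q / (12 + 16q + 12q²).

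| d | Expected true leavers | Leave before V2 | Leave between V2 and V3 | Leave after V3 |
|---|---|---|---|---|
| 2% | 0.8 | 31% | 40% | 29% |
| 5% | 1.9 | 32% | 40% | 28% |
| 10% | 3.6 | 33% | 40% | 27% |
| 20% | 6.5 | 37% | 39% | 24% |

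Example at d = 10%: 12 + 14.4 + 9.72 = 36.12; expected 0.1 × 36.12 = 3.6; middle share 14.4 / 36.12 = 40%.

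**Step 3: two ways to follow the labels.**

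- Count everyone who leaves between V2 and V3. This catches about 40% of true leavers. It also includes the V1-V2 and V3-V4 orders, so 8 of 24 (one third) of those counted are not between their own two VR sessions.
- Count only participants for whom both labels are right. This catches 4q / (12 + 16q + 12q²), about 10%, and nobody is counted wrongly.

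**Step 4: other schemes, counting everyone who leaves between V2 and V3.** A Williams or cyclic square gives a capture of about 33% or 50%, depending on how the letters are assigned. If the VR sessions are always paired at V1-V2 or V3-V4, capture is 0%. It is 100% only if every sequence is video-VR-VR-video.

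**The case against.** The strongest reply is that a careful analyst would not follow the labels. The text limits the measure to people who have had an initial VR session and compares scenes. To find the scene, the analyst must consult the REDCap assignment, which also shows which session was the first VR. On that reading the labels are a slip with little effect. Much of this stands: the one-third contamination in particular needs a reading that overrides the words initial and second. It does not remove the conflict, because the text does not say whether words or labels prevail.

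It is also fair that the percentages describe very few people. Missing 60% of 0.8 to 3.6 expected leavers means missing about 0.5 to 2, all still visible in the attendance data.

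A reader might infer two stronger claims that the documents do not support.

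*That unequal spacing biases the scene comparison.* The two VR sessions may be 1, 2 or 3 visits apart, and failure to return is 1 - (1 - d)^gap: 10%, 19% and 27.1% at d = 10%. With all 24 orders, however, gaps of 1, 2 and 3 visits occur 6, 4 and 2 times for each first scene, so they balance in expectation; they also balance in a Williams square. A marked imbalance arises in four of six labellings of a cyclic square (18 v 6 participants, gaps 1 v 3). There, with no scene effect, Fisher's test gives p ≤ 0.05 in 11.5% of trials at d = 10% and 21.7% at 20%, but only 3.3% at 5% and 0.3% at 2%. No section says that a cyclic square is used.

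*That the adherence aim or the safety data are compromised.* Adherence is measured by attendance at all four visits, which the labels leave untouched. Adverse events and incomplete VR sessions are recorded and summarised separately.

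**Conclusion.** The inconsistency is real, and the rule is wrong as written unless every sequence is video-VR-VR-video. That conclusion rests on the text alone. The figures of 4 of 24 and about 40% rest on equally likely orders, and the latter also on a constant leaving rate; both would change with the actual sequence list.

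The consequence is small: one descriptive comparison, few expected events, no decision rule attached. Severity is minor. Unequal spacing is something to check against the sequence list, not an established bias.

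**What to change.** Delete (V2) and (V3) from the Data Analysis Plan and identify each participant's first and second VR session from the REDCap assignment. Suggested text:

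> Among participants who receive a first VR session, at whichever visit it falls, the percentage who leave the study before their second VR session will be given by scene of the first VR session, with exact 95% confidence intervals and Fisher's exact test.

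If every sequence is in fact video-VR-VR-video, say so in the Design paragraph and keep the labels.

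Optional: check the sequence list for the number of visits between the two VR sessions. If it is not balanced across scenes, also report discontinuation before the next scheduled visit after the first VR session, as a supporting summary. That window exists for everyone, because the first VR session is never later than V3. It should not replace the plan's own question. With all 24 orders it sees only (12 + 8q + 4q²) / (12 + 16q + 12q²), or 60% to 65% of the relevant leavers at d = 2-20%, and it equalises the length of follow-up but not the visit at which it starts.

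The cost is one revised sentence. No new data are needed: REDCap issues the experience for each visit, and attendance is already collected.

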## **Participant Information**

**Target accrual:** 24 to be randomized (36 to be consented and screened).

**Participant population:** 24 adults

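### Early stopping and drop-out are analysed for VR only, with no video comparison, and the drop-out definition does not fit the randomised visit order

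*Combined protocol and SAP*

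**What the plan says.** All references are to the combined protocol and SAP.

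- **Role of the video (Video Experience Procedure).** "This process will provide a within-participant control, allowing us to investigate whether the VR experience is safe", and whether it produces more change than the video does.
- **Non-completion (Data Analysis).** Details will be summarised for participants with adverse events and for those who "are unable to complete the 10-minute VR experience for any reason". No matching item for the video appears anywhere.
- **Drop-out (Data Analysis).** "The percentage of participants who undergo the initial VR experience (V2) but discontinue study participation without returning for the" second VR, labelled V3, is the quantity that "will be summarized and compared between scenes using Fisher's exact test".
- **Attendance (Acceptability and Adherence to Intervention).** "Adherence to the R-VR will be assessed by collecting attendance for study visits 1-4". This covers video visits as well as VR visits.
- **Adverse events (Visit Flow and Timeline; Assessments).** The table marks them at each of the four experience visits, and the text describes symptom measures before and after.
- **Order (Study Design and Methods).** The order of the two VR scenes and two videos over Visits 1 to 4 is randomised. The set of sequences is not stated.
- **Size (Participant Information).** "24 to be randomized (36 to be consented and screened").

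**The concern.** Safety with acceptability, and adherence, are the first two primary aims, and the results are to inform whether a larger study with longer daily VR is developed. For that decision, a count of early stops or missed visits means little without knowing how often the same people stop or miss a video. Some busy staff can be expected to miss visits for reasons unrelated to the headset. The design supplies the comparator, but the analysis plan does not use it for these two measures.

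The drop-out definition adds two difficulties. It requires that a person "discontinue study participation without returning", so a missed second VR followed by a return is not an event. It also ties the two VR sessions to fixed visits, although the order is randomised.

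**Working it through.** **The plan's own figure.** N=24 cannot be reproduced. The Power Statement says only that it "was established after considering both the statistical implications and the amount of project effort and resources required", with no rate, alpha or power. The main check is therefore a comparison of definitions; the arithmetic only gives scale.

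**Step 1: what each measure covers.**

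| Measure | VR | Video | VR versus video planned? |
|---|---|---|---|
| Adverse events | collected | collected | not stated |
| Attendance | collected | collected | not stated |
| Session not completed | documented | no item | no |
| Drop-out percentage | first to second VR | not defined | no; scene versus scene only |

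**Step 2: the definition against the order.** Assume all 4! = 24 orders of four experiences are allowed. The two VRs can occupy 6 pairs of visits, each arising in 2 × 2 = 4 orders.

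- VR at exactly V2 and V3: 4 of 24.
- At least one video between the VRs (pairs 1-3, 1-4, 2-4): 3 × 4 = 12 of 24.
- A visit remaining after the second VR (pairs 1-2, 1-3, 2-3): 3 × 4 = 12 of 24.

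If V2 and V3 were instead taken literally for everyone, no video would lie between the VRs. V4 would still follow the second VR for every participant, so the omission would remain.

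**Step 3: illustrative attendance patterns.** The documents do not say which scene a drop-out is charged to; the scene of the first VR is the natural reading.

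| Assigned order | Attended | Planned drop-out percentage | Missed visits by assigned format | Last session before the first miss |
|---|---|---|---|---|
| VR, VR, video, video | V1, V3, V4 | not an event | VR 1 | VR |
| VR, video, VR, video | V1, V2, then leaves | event, charged to a VR scene | VR 1, video 1 | video |
| VR, video, VR, video | V1, V2, V4 | not an event | VR 1 | video |
| video, video, VR, VR | V1, then leaves | outside the denominator | video 1, VR 2 | video |

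The last two columns can disagree, so neither attribution is enough alone.

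**Step 4: what the scene test can show.** Assume 12 first-VR participants per scene and two-sided 0.05; neither is stated. For k versus 0 events, p = 2 × C(12,k) / C(24,k).

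- 4 versus 0: 2 × 495 / 10,626 = 0.093.
- 5 versus 0: 2 × 792 / 42,504 = 0.037.

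So at least 5 of 12 (42%) versus none is needed. Exact power over a range of assumed rates is 7% for 20% v 0%, 28% for 30% v 0%, 16% for 30% v 5%, 36% for 40% v 5% and 59% for 50% v 5%.

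**Step 5: precision of a VR-versus-video comparison.** Take each person as having or not having stopped early in each format, with n=24. An exact McNemar test gives p = 2 × 0.5^5 = 0.0625 for 5 versus 0 discordant people and 2 × 0.5^6 = 0.031 for 6 versus 0. With 0 of 24 events, the upper limit of the two-sided 95% interval is 1 − 0.025^(1/24) = 14.2%. The contrast is feasible, but the intervals will be wide.

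**The case against.** A reader might infer that drop-out is recorded for VR only and that tolerability has no video comparator at all. The documents do not support that. Attendance is collected at Visits 1 to 4, and REDCap holds the assigned experience, so a skipped VR visit can be identified. Symptoms such as dizziness and nausea are collected at video visits too and can be set against video. The only measure without a recording item is early stopping of the video.

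A reader might also take a skipped VR followed by an attended video as clear evidence of VR avoidance. That goes too far. Nothing says participants are told the next format. Where a visit remains after the second VR, they cannot deduce by elimination that VR is next. The documents do not describe skipping and resuming, either. The omission is a fault of definition, whatever the reason for the absence.

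Low power in a pilot that claims no power is not an error, and the section already promises point estimates with 95% confidence intervals throughout. Both points stand, so removing the Fisher test would be a preference.

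It could be said that the general repeated-measures sentence covers a VR-versus-video contrast. It follows the anxiety, stress and cognition outcomes, its examples are a paired t-test and repeated measures ANOVA, and it cannot supply a video measure that is not recorded.

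**Conclusion.** The point holds as a gap in the planned analysis and in the definitions, not as a general failure to collect data. Followed as written, the plan gives no video benchmark for non-completion or non-attendance. It leaves out people who miss only the second VR, and it can charge a departure that follows a video to a VR scene. The V2/V3 labels conflict with the randomised order and must be reconciled.

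Under the all-24-orders assumption, each of the two definitional problems can arise in half the sequences. How often either will occur cannot be known from the documents. The 5-versus-0 threshold rests on the assumed 12 v 12 split and two-sided 0.05; it shows only that a null scene result would say little about equal tolerability. The change is worth making before data collection, since video completion may not be recoverable afterwards.

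**What to change.** 1. Record completion (yes/no, with reason) for video sessions as for VR. Report the proportion of sessions stopped early by format, and the within-participant VR-minus-video difference with a 95% interval suited to small paired counts, for example a score interval for paired proportions.
2. From the attendance already collected, report missed visits by the format assigned to the missed visit and, separately, by the format of the last session attended. Using only the latter would charge a missed VR to the video before it.
3. Define VR non-return as having the first assigned VR and not the second, whether or not video visits are attended. Replace the V2/V3 labels with each participant's actual VR visits.
4. Report the scene comparison mainly as counts with an interval. If the Fisher test is kept, state that a non-significant result is not evidence of equal tolerability.

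The cost is a small REDCap addition for video sessions and some SAP wording. With 24 participants the intervals will be wide, and the report should say so.
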